7.1.2.5 Notification of Other Relevant Events

The subject should be instructed at the beginning of the study to inform the site immediately if subject has had or is scheduled to have any surgery which may remove some or all of her reproductive organs (i.e. hysterectomy, salpingectomy or oophorectomy)²⁹.

The subject will also be instructed to contact the Investigator immediately if, at any time during the study, subject thinks she might be pregnant.

If a subject experiences a micro-insert expulsion or removal during or following the NovaSure procedure, subject will be followed for the duration of the adverse event, then terminated from the study.

7.2 Population characteristics³⁰

7.2.1 Demographics

Demographic data collected include, but may not be limited to, date of birth (as allowed by local law), race, and ethnicity.

7.2.2 Medical history

Medical history findings (i.e. previous diagnoses, diseases or surgeries) meeting all criteria listed below will be collected³¹:

- Start before signing of the informed consent
- Considered relevant to the study.

Detailed instructions on the differentiation between (i) medical history and (ii) adverse events can be found in Section 7.4.1.1.

7.3 Efficacy

The primary variable is occurrence of confirmed pregnancy at 1 year and 3 years among subjects relying on Essure micro-inserts for permanent birth control when NovaSure is performed following a successful Essure Confirmation Test.

²⁸ Follow-up of adverse events was specified per Amendment 6.

²⁹ Here, a sentence was deleted per Amendment 4 (please see Section 13.2 for details).

³⁰ New section from sponsor template (Section 7.2 populated with content from previous version of protocol) per Amendment 4.

³¹ "Not pertaining to the study indication" was deleted per Amendment 5.

7.4 Safety³²

7.4.1 Adverse events

7.4.1.1 Definitions

7.4.1.1.1 Adverse event

In a clinical study, an AE is any untoward medical occurrence (i.e. any unfavorable and unintended sign [including abnormal laboratory findings], symptom or disease) in a subject or clinical investigation subject after providing written informed consent for participation in the study. Therefore, an AE may or may not be temporally or causally associated with the use of a medicinal (investigational) product or device.

7.4.1.1.1.1 Adverse device effect (ADE) - *amended*

An AE related to the use of Essure or NovaSure, including AEs resulting from insufficient or inadequate instructions for use, deployment, implant (placement), installation or operation or any malfunction of the investigational medical device, use error or from intentional misuse of the medical device.³³

7.4.1.1.1.2 Unanticipated adverse device effect (UADE)³⁴ - *amended*

A serious adverse effect is considered unanticipated if by its nature, incidence, severity or outcome it has not been identified in the IFU.

7.4.1.1.2 Serious adverse event (SAE)³⁵ - *amended*

An SAE is classified as any untoward medical occurrence that, at any dose, meets any of the following criteria (a – g):

- a. Results in death
- b. Is life-threatening

The term ‘life-threatening’ in the definition refers to an event in which the subject was at risk of death at the time of the event, it does not refer to an event which hypothetically might have caused death if it were more severe.

³² New section headings from sponsor template (Section 7.4 populated with content from previous version of protocol) per Amendment 4

³³ NovaSure added per Amendment 6.

³⁴ Per Amendment 4: The definition of UADE used in protocol version 3.0 (Conceptus) is consistent with the definition of USADE in this protocol version (4.0). The definition of UADE in this protocol version (4.0) only applies to non-serious events. This is corrected in Amendment 6 in accordance with 21 CFR 812.3(s).

³⁵ The definition of serious adverse event (SAE) was updated per Amendment 6.

- c. Requires inpatient hospitalization or prolongation of existing hospitalization

A hospitalization or prolongation of hospitalization will not be regarded as an SAE if at least one of the following exceptions is met:

- The admission results in a hospital stay of less than 12 hours
- The admission is pre-planned
(e.g. elective or scheduled surgery arranged prior to the start of the study; admission is part of the study procedures as described in Section 7.1.2)
- The admission is not associated with an AE
(e.g. social hospitalization for purposes of respite care).

However, it should be noted that invasive treatment during any hospitalization may fulfill the criterion of ‘medically important’ and as such may be reportable as an SAE dependent on clinical judgment. In addition, where local regulatory authorities specifically require a more stringent definition, the local regulation takes precedence.

- d. Results in persistent or significant disability / incapacity

Disability means a substantial disruption of a person’s ability to conduct normal life’s functions.

- e. Is a congenital anomaly / birth defect
- f. Is another serious or important medical event as judged by the investigator
- g. Requires intervention to prevent permanent impairment of a body function /damage, to a body structure

Note: For the purposes of this protocol, ectopic pregnancy and spontaneous abortion are always considered as important events and therefore reported as SAEs.

7.4.1.1.2.1 Incident

Any malfunction or deterioration in the characteristics and / or performance of a device, as well as any inadequacy in the labeling or the instructions for use which, directly or indirectly, led to, might lead to or might have led to the death of a patient, or user or of other persons or to a serious deterioration in their state of health.

Any event which meets all three basic reporting criteria (A-C) is considered an Incident:

- A. An event has occurred, e.g.
- malfunction or deterioration in the characteristics or performance
 - unanticipated adverse reaction or unanticipated side effect
 - interactions with other substances or products
 - degradation / destruction of the device
 - inappropriate therapy
 - inaccuracy in the labeling, instructions for use including omissions or deficiencies

- B) The device is suspected to be a contributory cause of the incident.
- C) The event led, or might have led, to one of the following outcomes:
- death of a patient, or user, or other person
 - serious deterioration in state of health of a patient, user or other person

(See European Commission, Medical Devices: Guidance document MEDDEV 2.12-1)

7.4.1.1.2.2 Unanticipated serious adverse device effect (USADE) - amended

An unanticipated serious adverse device effect (USADE) is any serious adverse effect on health or safety or any life-threatening problem or death caused by, or associated with, a device, if that effect, problem, or death was not previously identified in nature, severity, or degree of incidence in the investigational plan or application (including supplementary plan or application), or any other unanticipated serious problem associated with a device that relates to the rights, safety, or welfare of subjects. This is the same definition provided in the UADE Section 7.4.1.1.1.2. This has been corrected above in the UADE definition. However, as both terms have been used at various timepoints in this protocol, the definition is maintained here.³⁶

7.4.1.1.3 Medical Device Report (MDR) Reportable Event

- (1) An event that user facilities become aware of that reasonably suggests that a device has or may have caused or contributed to a death or serious injury; or
- (2) An event that manufacturers or importers become aware of that reasonably suggest that one of their marketed devices:
 - (i) May have caused or contributed to a death or serious injury, or
 - (ii) Has malfunctioned and that the device or a similar device marketed by the manufacturer or importer would be likely to cause or contribute to a death or serious injury if the malfunction were to recur.

(See 21 CFR 803 Medical Device reporting)

An MDR corresponds to the definition of Incident.

7.4.1.1.4 Device deficiency - amended

Inadequacy of Essure or Novasure related to its identity, quality, durability, reliability, safety or performance, such as malfunction, misuse or use error and inadequate labeling.³³

7.4.1.1.4.1 Device failure - amended

Failure of Essure or Novasure to perform or function as intended, including any deviations from the performance specifications or intended use (e.g., pregnancy when micro-insert properly located and fallopian tubes occluded; continued menorrhagia despite a completed endometrial ablation procedure). For the purposes of this study, a pregnancy that occurs in a subject told to rely on a commercially available Essure device for contraception is a device

³⁶ Modified per Amendment 6, see Section 7.4.1.1.2 UADE.

failure. For the purposes of this protocol, persistence or recurrence of heavy menstrual bleeding will be considered device failures for the Novasure device.³³

7.4.1.1.4.2 Device malfunction - amended

Failure of Essure or Novasure to meet its performance specifications or otherwise perform as intended when used in accordance with the IFU (e.g., difficulties with deployment or detachment of micro-insert; device difficulties when conducting endometrial ablation).³³

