1.5.2 Commercial Reports

Data on the commercial and compatible use of NovaSure EA with Essure micro-inserts in place have been reported. D. Saunders conducted a retrospective case review study of 118 sequential patients who had Essure micro-insert placement followed by NovaSure endometrial ablation. The interval between the Essure placement and NovaSure procedures ranged from 2 to 108 days. All patients were informed of the Essure Instructions for Use requirements for the Essure Confirmation Test to be performed 90-days after micro-insert placement; most patients chose not to wait because of their desire for the NovaSure endometrial ablation to eliminate their excessive uterine bleeding sooner. Two patients required replacement of the micro-insert at the time of the NovaSure procedure because the micro-insert was attached to the NovaSure instrument when it was withdrawn. A second

device was placed without difficulty. At up to two years of follow up (for the earliest study participant), none of the study subjects have had a pregnancy. No complications occurred and no adverse events have required treatment or hospitalization [[4]].

Basinski, et al, conducted a retrospective review of 117 patients who had undergone Essure micro-insert placement followed by NovaSure in two in-office sessions separated by a median time of 14 days. In this study, 83/117 (71%) returned for the Essure Confirmation Test. Satisfactory placement and tubal occlusion was demonstrated in 79/83 (95%) of these patients. Amenorrhea or spotting was observed in 72/97 (74%) of patients, 22/97 (23%) reported satisfactory decrease in menstrual flow, and 3/97 (3%) patients reported failure of the ablation procedure. A total of eight adverse events was obtained on 111/117 (95%) patients that had follow up. None of the adverse events reported in the study appeared to be related to the performance of NovaSure after Essure specifically. There have been no reported pregnancies for the patients that have been relying on Essure for permanent contraception from 6 to 24 months. The study results showed that the combination of Essure followed by NovaSure did not decrease effectiveness of either procedure and no serious adverse events were attributed to the combination of the two procedures in this study [[5]].

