7.1.2.3 One-Week Post-NovaSure EA Office Visit (\pm 2 days)

One week (plus or minus two days) from the date of NovaSure EA, the subject will return to the physician's office. At that time, designated study staff will conduct the following assessments:

- Physical Exam (Vitals)
- Inquire whether or not any adverse events occurred since the NovaSure procedure
- Conduct subject interview to obtain information on subject satisfaction and comfort with wearing the Essure micro-inserts post-NovaSure EA
- Confirm subject contact information
- Discuss any additional issues subject or the Investigator may have

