7.1.2.4 One-, Two- and Three-Year Post-EA Phone Call (\pm 28 days) - *amended*

One, two-, and three- years (\pm 28 days) from the date of the NovaSure EA procedure, the subject will be contacted by the physician's office to have a telephone follow-up visit. During each of these visits, designated study staff will conduct subject interview to:

- Confirm subject is not currently pregnant or has not been pregnant in the previous year
- Inquire whether or not any adverse events occurred over the past year
- Conduct subject interview to obtain information on subject satisfaction and comfort with wearing the micro-inserts post-NovaSure EA procedure
- Discuss whether or not subject has had or will have any extirpative surgery
- Confirm subject contact information
- Discuss any additional issues subject or the Investigator may have

The 3-year phone call will be the final visit in the study. If the subject reports a serious adverse event or pregnancy during the 3-year follow-up phone call, the subject will be followed by the sponsor's pharmacovigilance department until event resolution or stabilization. If a pregnancy or serious adverse event was previously reported but the event is not resolved during the 3-year phone call, the event will be followed by the sponsor's

²⁷ Per Amendment 4

pharmacovigilance department until resolution. Information pertaining to these events will be collected and archived in the sponsor's pharmacovigilance database.²⁸

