7.4.1.4 Reporting of serious adverse events - amended

The definition of serious adverse events (SAEs) is given in Section 7.4.1.1. These include device deficiencies that may have led to a SAE if a) suitable action had not been taken or b) intervention had not been made or c) if circumstances had been less fortunate. These are handled under the sponsor's SAE reporting system.

Investigator's notification of the sponsor

All investigators will be thoroughly instructed and trained on all relevant aspects of the investigator's reporting obligations for SAEs. This information, including all relevant contact details, is summarized in the investigator site file. This information will be updated as needed.

All SAEs and SADEs occurring during the observation period defined in Section 7.4.1.3 must immediately (within 24 hours of the investigator's awareness) be reported to the sponsor.⁴⁰ An SAE form must also be completed within 24 hours of the investigator awareness and forwarded to the sponsor's designated recipient.

Each SAE and incident must be followed up until resolution or stabilization by submission of updated reports to the designated recipient. Any SAE or incident occurring after the protocol-defined observation period will be processed by the sponsor according to all applicable regulations.

³⁸ Section was updated per Amendment 6.

³⁹ Per Amendment 5

⁴⁰ Sentence modified per Amendment 6.

In addition, device failures, malfunctions or incidents must be reported to Sponsor within 24 hours via fax or email.

Ectopic pregnancies and spontaneous abortions will always be considered as SAEs and reported as such to the Sponsor

Notification of the independent ethics committee (IEC)s / institutional review board (IRB)s

Notification of the IECs / IRBs about all relevant events (e.g. SAEs, incidents, UADEs, device failures, device malfunctions) will be performed by the investigator according to all applicable regulations.

Notification of the authorities

The processing and reporting of all relevant events (e.g. SAEs, incidents, UADEs, device failures, device malfunctions) to the authorities will be done by the sponsor according to all applicable regulations.

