6.3.1.1 Adverse Device Events

All adverse device events that are also adverse events constitute adverse device effects (ADEs). ADEs are defined as AEs that are at least possibly related to the Essure or NovaSure device/procedure)

All adverse device effects (ADEs) will be summarized for the primary safety cohort. All ADEs will be coded using MedDRA.

Frequency tables showing an overall summary of the number of events (where possible) and the number of subjects with ADEs by system organ class (SOC) and preferred term (PT) will be given for the following types of ADEs:

- All adverse device events
- Adverse device events leading to AEs
- ADEs that are serious adverse events (SAEs)
- Adverse device events that could lead to SAEs
- Adverse device events by category (device deficiency, device failure, device malfunction, medical device report (MDR) reportable event, important medical events and events of special interest, unknown, and other)

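### NovaSure failure is defined by persistent or recurrent heavy bleeding and is tabulated, but no listed assessment asks about bleeding, so the count is likely incomplete and is not a failure rate

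*Protocol*

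**What the plan says.** Protocol 7.4.1.1.4.1 gives each device its own failure. For Essure it is pregnancy in a woman told to rely on the device. For the ablation device, "persistence or recurrence of heavy menstrual bleeding will be considered device failures for the Novasure device".

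Such failures are meant to be recorded and reported. Protocol 7.4.1.3 has investigators document all of them on a Device Malfunction and Failure form, and 7.4.1.4 adds that "device failures, malfunctions or incidents must be reported to Sponsor within 24 hours via fax or email". SAP 6.3.1.1 then plans frequency tables of "Adverse device events by category (device deficiency, device failure, device malfunction" and further categories, and specifies that "ADEs are defined as AEs that are at least possibly related to the Essure or NovaSure device/procedure".

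The follow-up contacts ask for the following:

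- One week (7.1.2.3): "Inquire whether or not any adverse events occurred since the NovaSure procedure", with a physical exam and an interview on satisfaction and comfort.
- One, two and three years (7.1.2.4): "Inquire whether or not any adverse events occurred over the past year" and "Conduct subject interview to obtain information on subject satisfaction and comfort with wearing the micro-inserts post-NovaSure EA procedure", plus pregnancy status, removal surgery and any other issues.

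**The concern.** The plan defines an outcome, requires that it be reported and gives it a table category, but specifies no assessment aimed at it. The contrast with Essure is plain: pregnancy has its own row in Table 7–1, as does removal surgery. Amendment 6 extended the failure definition to NovaSure and also revised the text of the annual calls, without adding a bleeding item.

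The general adverse event question is a weak substitute for this outcome in particular. Menorrhagia is an entry criterion (5.1.1). A woman whose bleeding recurs after a good interval has something new to mention. A woman whose bleeding never improved may not think of it as something that happened in the past year, and a site may not record a condition that began before consent as an adverse event.

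At stake is how the device-failure row can be read. Protocol 1.5.3 says that the larger earlier studies showed no effect of the inserts on ablation performance. A low failure count, with no number of women asked beside it, could be taken as support for that statement when it partly reflects what was not asked.

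**Working it through.** **1. Is there a figure in the plan to reproduce?** No. The documents state no NovaSure failure rate, target or sample size. The check is a comparison of texts, followed by an illustration of size.

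**2. Where could a bleeding failure be picked up?**

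| Place | Content | Specific to bleeding? |
|---|---|---|
| Table 7–1 | Rows for pregnancy status, adverse events, removal surgery, interview | No |
| Protocol 7.1.2.3, one week | Exam, adverse events, satisfaction and comfort, other issues | No |
| Protocol 7.1.2.4, annual calls | Pregnancy, adverse events, satisfaction and comfort, surgery, other issues | No |
| SAP 6.1 and 6.2.3.1, follow-up variables | Insert expulsion (6.1 only), comfort, satisfaction with the insert, satisfaction with the combined treatment plan | No |
| SAP 6.3.1, special-interest events | Abnormal uterine bleeding group | Groups reported adverse events; asks nothing |

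The last row does not isolate failure either. The group pools menorrhagia with amenorrhoea, hypomenorrhoea and oligomenorrhoea. The retrospective series cited in Protocol 1.5.2 reports amenorrhoea or spotting (72/97) separately from ablation failure (3/97), so the group total can mix opposite results of the ablation.

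**3. What must happen for a failure to be counted?** The bleeding must come to the site's notice and be recorded. To count as an adverse device effect under SAP 6.3.1.1, it must also be an adverse event judged at least possibly related to a device or procedure. Each step can lose cases.

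**4. Illustration of size.**

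Inputs:

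- N = 220, the minimum enrolment (Protocol section 4).
- p = 3/97, the only ablation failure figure in the documents: "3/97 (3%) patients reported failure of the ablation procedure" (Protocol 1.5.2).
- s = the share of failures that surface without a bleeding question. The documents do not give it; 80%, 50% and 25% are assumed.

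Failure proportion: 3/97 = 3.1%. The exact (Clopper–Pearson) 95% interval has as limits the 2.5% point of beta(3, 95) and the 97.5% point of beta(4, 94), which are 0.64% and 8.77%.

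Expected reported failures = N × p × s. For example, 220 × 0.0309 × 1 = 6.8 and 220 × 0.0309 × 0.5 = 3.4.

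| s | p = 0.64% | p = 3.09% | p = 8.77% | Apparent rate at p = 3.09% |
|---|---|---|---|---|
| 100% | 1.4 | 6.8 | 19.3 | 3.1% |
| 80% | 1.1 | 5.4 | 15.4 | 2.5% |
| 50% | 0.7 | 3.4 | 9.7 | 1.5% |
| 25% | 0.4 | 1.7 | 4.8 | 0.8% |

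A reported count of 3 or 4 would fit a true rate near 3% with half the cases missed, or a true rate near 1.5% with none missed. Without knowing how many women were asked, the table cannot separate the two.

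**The case against.** The strongest reply is that other routes exist and that the interview wording is not in these documents.

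- Every post-procedure contact includes an adverse event inquiry and an invitation to raise other issues, and removal surgery is asked about yearly.
- Satisfaction with the whole treatment plan, NovaSure included, is rated at each follow-up, which invites a comment on a failed ablation.
- The office making the calls is the one where the woman sought treatment for menorrhagia.
- The adverse event definition (7.4.1.1.1) contains no new-onset requirement, and the SAP lists menorrhagia among its special-interest terms.
- The protocol's visit lists are not exhaustive: SAP 6.1 summarises an insert-expulsion item at every follow-up that 7.1.2.3 and 7.1.2.4 do not list. A bleeding item could likewise sit on the unattached forms.

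Much of this stands. A reader might infer that no visit asks about bleeding at all and that the count is bound to be too low. The documents do not support that. They show that no bleeding question is specified, not that none is asked, and they give no capture share. What survives is that the SAP, which does list the expulsion item, lists no bleeding variable at any time point. The duty to document failures also cannot reach failures that a site never hears of.

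A reader might also infer that the plan means to use this table to show that the inserts leave ablation unimpaired. No section proposes that. The table is descriptive, the study has one arm, and ablation effectiveness is not a named endpoint.

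Finally, 3/97 comes from a retrospective series in which NovaSure followed Essure by a median of 14 days, not after a three-month confirmation test. It is a guide to scale only.

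**Conclusion.** The point holds as one of likely incomplete ascertainment. The plan defines and tabulates NovaSure failure but specifies no question that would find it, and persistence is the part most exposed. As planned, the count should be read as a lower bound on the number of women with failure, provided that the failures reported are correctly classified. It should not be read as a rate.

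The direction is a reasoned expectation; the size is unknown. With the cited series as a guide, full capture would give about 7 of 220 women (1 to 19), and the shortfall depends entirely on the assumed share that surfaces. The primary analysis, its threshold and the success criterion all concern pregnancy and are untouched. This is a cheap improvement, not a threat to the study's main conclusion.

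**What to change.** 1. Add one item to each annual call in Protocol 7.1.2.4 and Table 7–1: whether heavy menstrual bleeding has persisted or recurred since NovaSure or since the last contact, and whether any repeat treatment for bleeding was given. Asking about the interval, not only current status, also catches a recurrence that resolved between calls.
2. Classify failures by the existing definition in 7.4.1.1.4.1. A comparison scale that counted only unchanged or heavier bleeding would depart from it, because bleeding that is lighter but still heavy is persistence.
3. In SAP 6.3.1.1, show NovaSure failures separately from Essure failures, with the number of women asked as the denominator.
4. For calls already completed, state in the SAP that the NovaSure failure count comes from unprompted reports and is a lower bound. This may cover most calls: SAP version 1.1 is dated 15 December 2020, and Protocol section 15 expected final follow-up in January 2021.

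Cost: one form field, a protocol amendment at up to 30 sites and one or two SAP lines; if the calls are finished, only the SAP sentence in step 4. The downside is that the NovaSure failure count will probably look less favourable.
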